Standard questions from our pilot studies will be used to assess demographics, medical history/update, psychiatric history/update, and current medications. Depression care variables (e.g., dose and duration of antidepressants, # and type of psychotherapy sessions) will be extracted from the treatment notes for eIMPACT patients. To obtain additional depression care data, all patients will complete a brief interview at the mid- and post-treatment visits and during the follow-up calls. Consistent with approved Authorization Form for this study, we will also periodically extract relevant depression treatment data (e.g., dose and duration of antidepressants) from the electronic medical record for all patients. We will also assess anxiety symptoms using the Generalized Anxiety Disorder-7 (GAD-7),²⁰⁰ hostility/anger using the Buss-Perry Aggression Questionnaire,²⁰¹ trait positive affect using the Positive Affect subscale of the Positive and Negative Affect Schedule (PANAS),^{202,203} and sleep quality using the Pittsburgh Sleep Quality Index,²⁰³ all of which are widely used and validated instruments. We will also assess depression treatment satisfaction using an item employed in other recent depression trials conducted on the IUPUI campus and for the occurrence of any potential adverse events using a brief questionnaire. Finally, the Regenstrief programmer will identify potential adverse events by searching the INPC every 6 months (before DSMB meetings) for emergency department visits, hospitalizations, and deaths.

All items of the questionnaires to be administered at the pre-treatment visit (see Appendix 2), mid-treatment visit (see Appendix 3), post-treatment visit (see Appendix 4), and annual follow-up calls (see Appendix 5) can be found in the appendices.

Suicidal Ideation Protection Protocol

For the entire protocol, see Appendix 6.

6.0 Reporting of Adverse Events or Unanticipated Problems involving Risk to Participants or Others

We have developed a Data and Safety Monitoring Plan and Board to ensure the safety of participants and to monitor data quality and participant recruitment, accrual, and retention.

Data and Safety Monitoring Plan:

- If an adverse event occurs, its severity will be promptly graded using the following scale:
 1. Mild: Awareness of sign or symptom but easily tolerated
 2. Moderate: Interference with normal daily activities
 3. Severe: Inability to perform normal daily activities

4. Life Threatening: Immediate risk of death from the reaction as it occurred

- After grading severity, the attribution of the adverse event will be graded using the following scale:
 - Definite: Adverse event clearly related to study involvement
 - Probable: Adverse event likely related to study involvement
 - Possible: Adverse event may be related to study involvement
 - Unlikely: Adverse event doubtfully related to study involvement
 - Unrelated: Adverse event clearly not related to study involvement
- All adverse events that meet the IUPUI IRB prompt reporting requirements (i.e., unexpected, related or possibly related to participation in the research, and suggest that the research places subjects or others at a greater risk of harm than was previously known or recognized) will be reported to the IUPUI IRB, CRC Research Subject Advocate, and NIH immediately. All other adverse events will be reported to these entities at the time of continuing review.
- A summary of adverse event data (frequency, types, and corrective actions) will be provided to the IUPUI IRB, CRC Research Subject Advocate, and NIH at the time of continuing review.

Data and Safety Monitoring Board:

- A 4-member, independent Data and Safety Monitoring Board (DSMB) will be formed to provide independent oversight. The DSMB will consist of a psychiatrist (from the Indiana University Department of Psychiatry), a cardiologist (from the Indiana University Krannert Institute of Cardiology), a clinical trialist (from the Indiana University Department of Biostatistics), and a medical ethicist (from the Indiana University Center for Aging Research), all of whom will not be part of the study team.
- Adverse events that are severe, life-threatening, or unanticipated will be immediately reviewed by the DSMB. At 6-month intervals, the DSMB will prepare a formal report of participant recruitment, accrual, retention, data quality, and adverse events. At that time, the DSMB will also determine whether the study should continue unchanged, be modified, or be stopped. The IUPUI IRB, CRC Research Subject Advocate, and NIH will receive copies of all DSMB reports at the time of continuing review.

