We will leverage this unique resource to identify CVD events. The Indiana Network for Patient Care (INPC),^{117,118} the nation's largest clinical data repository (see Facilities and Other Resources), was an NIH-funded expansion of the Regenstrief Medical Record System,¹¹⁹ which has been used extensively for clinical research. The INPC contains 4.7 billion bits of standardized clinical data for 14.7 million patients from 19,000 physicians, 90 hospitals, and 110 clinics and other sites. The participating systems deliver registration records; coded diagnoses and procedures; laboratory, pathology, and vital signs data; emergency department, inpatient, and outpatient encounter data; and pharmacy data. INPC also gathers data from Indiana Medicaid and other commercial payers, as well as death data from the Indiana State Department of Health.

Advantages of our approach include minimal attrition and an observation period that can be easily extended. As in our IMPACT follow-up study,³⁵ we anticipate having event data for nearly all randomized patients, given that (a) we will identify most CVD events through INPC searches (no patient participation required) and (b) we have developed procedures (e.g., follow-up calls) to identify the few events that may occur outside of the INPC

catchment area. Extending the observation period to capture more CVD events would also require few resources, as it would involve the data manager re-running INPC search programs.

Proposed Research and Conceptual Framework

We will conduct a Phase 2 randomized controlled trial of 220 primary care patients aged 50+ years with a depressive disorder and CVD risk factors but no clinical CVD. Patients will be randomized to 12 months of eIMPACT or usual care and will be followed for a mean of 4 years. The conceptual framework guiding our trial is shown in Figure 1. Our central hypothesis is that eIMPACT will improve endothelial dysfunction by decreasing depressive symptoms, autonomic dysfunction, systemic inflammation, and platelet activation.

[figure not shown]

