The timing of activities is shown in the table below. We will strive to schedule patients within two weeks of enrollment, although some visits will fall outside of that window due to conflicts in the patients' schedules and no-showed or rescheduled appointments. Patients will attend a 3-hour pre-treatment visit at the Indiana CTSI Clinical Research Center. To minimize the effect of extraneous factors on FMD,^{169,170} patients will be told to fast and to avoid tobacco and exercise for ≥ 8 hours before their visit. The exam room will be kept at 68-71°F, and premenopausal women will be scheduled within 2 weeks of menstruation onset. Patients will have their height, weight, and BP measured; will complete self-report scales on a secure SurveyMonkey website designed for this study visit; and will undergo FMD and heart rate variability assessments and a blood draw (standard venipuncture). To end this visit, the randomization procedure will be initiated, the patient and the treatment team will be notified of the assignment, and the mid-treatment call and post-treatment visit will be scheduled. If the patient is randomized to the eIMPACT intervention, the depression clinical specialist will conduct a brief session over FaceTime to orient the patient to intervention materials and to schedule the initial assessment. The FaceTime session will not be recorded. Within 2 weeks, the depression clinical specialist will call eIMPACT patients to initiate treatment, and a research assistant will send a letter to the primary care providers of usual care patients to notify them that their patient has a depressive disorder and to encourage follow-up. Approximately six months after randomization, research assistants will contact all patients to complete the 45-min mid-treatment call. First, a brief questionnaire used in our pilot trials will be administered to assess for the occurrence of CVD events since enrollment. As we have also done in our pilot projects, the self-reported scales completed at pre-treatment will then be readministered. Approximately twelve months after randomization, patients will return to the Clinical Research Center for the post-treatment visit, during which all factors measured at pre-treatment will be reassessed. Finally, research assistant will contact patients annually after their post-treatment visit to complete the follow-up calls, with the last call coming within 2 weeks of the study end date. These calls will follow the same procedures as the mid-treatment call.

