Our exploratory outcome, modeled after the JUPITER trial,¹⁹⁵ is time to first major CVD event, defined as: CVD death (ICD-10 I20-I25 or I60-I69 the first-listed cause of death); nonfatal MI (CK-MB >3.0 ng/ml, troponin >0.3 µg/L, or ICD-9 410); nonfatal stroke (ICD-9 430-432, 433.01, 433.11, 433.21, 433.31, 433.91, 434.01, 434.11, 434.91); unstable angina requiring hospitalization (inpatient admission ICD-9 411.1); and revascularization – i.e., percutaneous coronary intervention (ICD-9 00.66, 36.03, 36.06, 36.07, 36.09; CPT 92980-92984, 92995, 92996) or coronary artery bypass graft (ICD-9 36.10-36.19; CPT 33510-33536). Because recruitment will occur during Years 01-02, the mean observation period will be 4 years (1-year intervention period plus 3-year follow-

up period), with a range of 3-5 years. The Regenstrief programmer who worked on our IMPACT study³⁵ will identify candidate CVD events by searching the INPC every 6 months (blind to assignment), with the last search performed on the end date. To capture the small number of events that may occur outside of the INPC catchment area, patients will complete a CVD questionnaire at mid- and post-treatment and during the follow-up calls. If a reported event is not in the INPC, we will request medical records from the patient to confirm the event. Our cardiologist ([name]), also blinded, will use standardized criteria to adjudicate all CVD events for this exploratory outcome. [name] has served on endpoint committees for past trials. When needed, [name] will consult with the cardiologist on the DSMB (also blinded). Given that we are coding “harder” events and that many events will be positive for multiple markers, it is unlikely that coded events will be misclassified. We may fail to detect (and thus initially misclassify) a few events through INPC, which is why we are obtaining patient reports and medical records.

Atherogenic Behavioral Factors

The BRFSS Tobacco Use Questionnaire, International Physical Activity Questionnaire, and the Morisky Questionnaire (MMAS-8) will assess tobacco use, physical activity, and adherence to cholesterol and blood pressure medications, respectively. Each scale possesses strong psychometric properties.¹⁹⁶⁻¹⁹⁸

Conventional CVD Risk Factors

SBP and DBP will be the mean of the last 2 of 3 readings.¹⁹⁹ Fasting cholesterol, glucose, insulin, and HbA1c will be quantified using standard methods. BMI will be computed from measured height and weight.

Miscellaneous Factors

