We will use the intent-to-treat approach.²⁰⁸ All tests will be two-tailed with $p < .05$ considered significant. Supplemental analyses of completers will be performed. We will assess for differences in all baseline factors. Due to randomization, we do not expect baseline group differences. Even so, any differences will be taken into account when interpreting results, and any baseline factors that differ between the groups will be included as covariates in sensitivity analyses. Aim 1: We will test our hypothesis that eIMPACT patients will exhibit greater improvement in endothelial dysfunction (Hypothesis 1) by performing a two-sample t-test with FMD at 12 months as the dependent variable. If there is a group difference in baseline FMD, analyses of covariance (ANCOVAs) adjusting for baseline level will also be performed. We will also explore whether eIMPACT patients show a clinically relevant reduction (25% lower relative risk) in CVD events by running a Cox proportional hazards model with treatment group predicting time to first CVD event. Patients will be censored at non-CVD death or the end date. We expect to observe a $HR \leq 0.75$. Aim 2: We will test our hypotheses that eIMPACT patients will exhibit greater decreases in the candidate mechanisms (Hypotheses 2-5) by performing two-sample t-tests with SCL-20 score, high-frequency heart rate variability, IL-6, CRP, BTG, and PF4 at 12 months as the dependent variables. If baseline group differences are found, ANCOVAs adjusting for baseline level will

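### The final INPC search falls on the censoring date with no allowance for late-posted records, so some CVD events just before the end date, deaths above all, can be missed

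*Combined protocol and SAP*

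**What the plan says.** Section 5.0 (CVD Events) defines the exploratory outcome as time to first major CVD event. A programmer will "identify candidate CVD events by searching the INPC every 6 months", "blind to assignment), with the last search performed on the end date". Section 8.0 (Statistical Analyses) sets the end of follow-up for the Cox model: "Patients will be censored at non-CVD death or the end date".

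The components rest on different kinds of record. Fatal events are "CVD death (ICD-10 I20-I25 or I60-I69 the first-listed cause of death"); Section 1.0 says the INPC draws on hospital, payer and other feeds "as well as death data from the Indiana State Department of Health". Nonfatal stroke, unstable angina requiring admission and revascularization are defined by diagnosis or procedure codes alone. MI also has a laboratory route: "nonfatal MI (CK-MB >3.0 ng/ml, troponin >0.3 µg/L, or ICD-9 410").

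There is a second source. Patients answer a CVD questionnaire at mid-treatment, post-treatment and each annual call, "with the last call coming within 2 weeks of the study end date". Medical records are requested for any reported event that the INPC does not show, and a blinded cardiologist adjudicates all events. Section 5.0 admits that the INPC may miss a few events and gives patient reports and records as the answer.

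**The concern.** A search can find only what has been posted by the day it is run. Each 6-monthly search is corrected by the next one, but the last has no successor. Because it coincides with the censoring date, a patient whose event has occurred but is not yet coded, or whose cause of death is not yet registered, enters the Cox model as event-free to the end date.

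The patient calls narrow this gap without closing it. Their stated purpose is to catch events outside the INPC catchment area, not late posting. The last call may come before or after the end date; if before, up to 2 weeks are uncovered. A patient who has died cannot report. Under Section 7.0, patients withdrawn for serious illness complete no further calls although their record data may still be collected with permission, so for them the records are the only source.

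At stake is a small loss of events from an outcome with few of them, and a cumulative rate that reads low to anyone who later uses it for planning.

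**Working it through.** **Inputs from Section 8.0 (Sample Size):** 20% cumulative event rate over a mean of 4 years, 194 patients with event data, 39 events, HR 0.75. **From Section 5.0:** follow-up ranging from 3 to 5 years. **Assumed:** constant hazard, uniform entry, equal arms, and the posting delay, for which the documents give no figure; 1, 3 and 6 months are shown as a range.

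**Plan's own figure.** 0.20 × 194 = 38.8, which rounds to the stated 39. (The plan's 194 is slightly below 0.90 × 220 = 198; I use 194 as stated.)

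**Events per unit time near the end date.**
- Hazard = −ln(0.80)/4 = 0.0558 per year.
- Still event-free at the end, averaged over follow-up t of 3 to 5 years: 194 × mean of exp(−0.0558 t) ≈ 155.
- Rate near the end: 155 × 0.0558 ≈ 8.7 events per year.
- Events in the final window = 155 × 0.0558 × months/12, with unrounded inputs: 0.72 for 1 month, 2.17 for 3 months, 4.33 for 6 months.
- As a share of 39: 2%, 6% and 11%.

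**Check with a two-arm model.** Take 97 patients per arm and set the usual-care hazard so that HR 0.75 yields 38.8 events in total. This gives 0.0641 per year in usual care (21.9 events) and 0.75 × 0.0641 = 0.0480 in eIMPACT (16.9 events). Treat every event in the final window as undetected and count those patients as event-free to the end date. The cumulative rate is detected events divided by 194; power is the Schoenfeld approximation, two-sided 0.05.

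| Assumed delay | Events undetected (at most) | Events left | Cumulative rate | Expected rate ratio | Power for HR 0.75 |
|---|---|---|---|---|---|
| none | 0 | 38.8 | 20.0% | 0.750 | 0.144 |
| 1 month | 0.7 | 38.1 | 19.6% | 0.750 | 0.142 |
| 3 months | 2.2 | 36.6 | 18.9% | 0.749 | 0.138 |
| 6 months | 4.4 | 34.4 | 17.7% | 0.748 | 0.132 |

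The two calculations agree to within 0.1 event. Both are upper bounds, because they suppose that every component is delayed and that nothing is found by another route.

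**A narrower figure for deaths.** The documents give no fatal share. If 10% to 40% of events were CVD deaths (assumed), a 3-month delay would hide 0.10 × 2.2 = 0.2 to 0.40 × 2.2 = 0.9 deaths, and a 6-month delay 0.10 × 4.3 = 0.4 to 0.40 × 4.3 = 1.7. If the last call precedes the end date by as much as 2 weeks, that window holds about 0.4 events of all kinds (0.36 in the two-arm model at half a month).

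**The case against.** The strongest reply is that the loss is possible but not shown. No posting or certification delay appears anywhere in the documents. The INPC also receives laboratory and encounter data, MI can be identified from CK-MB or troponin without any code, and Section 5.0 expects many events to be positive on several markers. The record-request rule applies whatever the reason an event is absent from the INPC, so a reported but uncoded event would be pursued. The separate 6-monthly safety search for emergency visits, hospitalizations and deaths may add a little, though it uses the same source.

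All of that stands. A reader might infer from the coinciding dates that late events will be lost, or that a tenth of the events will be. The documents support neither: the 11% needs a 6-month delay in every component and a failed back-up.

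A reader might also infer a distorted treatment comparison. With equal delay in both arms the expected rate ratio moves only from 0.750 to 0.748, and nothing in the documents points to unequal delay. The outcome is exploratory, and Section 8.0 says that the trial is not designed to detect a significant difference in events. Even the 3-month shift in the cumulative rate, 20.0% to 18.9%, is small beside its sampling standard error of √(0.2 × 0.8/194) = 2.9 percentage points. Section 1.0 says Phase 3 planning will combine this trial's effect estimates with those of other studies; it does not name this trial's event rate as the input.

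The reply does not reach late CVD deaths, events that a patient cannot or does not report, or events after a last call made before the end date.

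**Conclusion.** The point holds as a modest, easily repaired weakness. As written, the rules allow CVD events shortly before the end date to be recorded as event-free follow-up, and deaths are the most exposed. For assumed delays of 1, 3 or 6 months the ceiling is about 0.7, 2.2 or 4.3 of 39 events; the true loss would be smaller by whatever laboratory results and the last call recover. The consequence is a slightly low event count and cumulative rate for an exploratory outcome. There is almost no bias in the hazard ratio provided the delay is equal in both arms, power that is already about 0.14 barely changes, and the 12-month FMD analysis is untouched. The size depends on a delay that only the data source can supply.

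**What to change.** Keep the end date as both the event cut-off and the censoring date. Run the final INPC and death-data search after a pre-specified delay confirmed with the data source, for example 3 months, and longer for cause of death if needed. Count only events dated on or before the end date. Make the last call on the end date or within the 2 weeks after it. Lock the event file once that search has been adjudicated. State this in advance, so that a decision to search again is not taken after results are known.

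The cost is one more run of an existing program. Section 1.0 says that extending observation needs few resources, "as it would involve the data manager re-running INPC search programs"; the same program would serve here. The downside is that the event analysis locks a few months later.

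If the end of funding rules this out, an earlier, data-complete cut-off would align events with person-time and so give an unbiased rate. It would recover no events, and the stated mean follow-up of 4 years would have to be shortened by the same interval.

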7.0 Study Withdrawal/Discontinuation

All participants will be considered enrolled at the end of the ResNet interview. The informed consent statement describes the possibility of and the procedures for withdrawing from the study. A participant may notify either the principal investigator or any member of the research team at any time via email, phone, or in-person that s/he wants to withdraw from the study for any reason. The schedule of participant reimbursement is as follows: \$100 for the pre-treatment visit, \$25 for the mid-treatment call, \$100 for the post-treatment visit, \$20 for each of the annual follow-up calls, and up to \$10 per visit to cover parking or transportation costs. If a participant withdraws before the pre-treatment assessment visit, no payment will be provided.

Other reasons for study withdrawal/discontinuation are (a) the participant's primary care provider or another provider seeing the participant (e.g., a psychiatrist outside of the study team) no longer believes that his/her patient is appropriate for this trial after a triggering of the Suicidal Ideation Protection Protocol or any other reason, (b) the participant develops acute or serious illness that precludes completion of the main study visits within the allowed timeframes, and (c) the participant, in the assessment of the eIMPACT psychiatrist, exhibits evidence of a psychotic disorder or bipolar disorder (both of which are exclusionary conditions and could interfere with treatment delivery/effectiveness) during the 1-year treatment phase of the trial. In the case of situation (b), the patient will not complete any future study visits or calls. However, if the patient provides permission, electronic medical record data (e.g., incident CVD events) will still be obtained going forward, consistent with our Authorization Form. In the case of situation (c), patients with a psychotic disorder or bipolar disorder would likely benefit from psychotropic medications, such as antipsychotic medications or mood stabilizer, that are beyond what are provided in this trial.

For Usual Care patients who score in the "severe depression" range (20-27) on the PHQ-9 at the mid-treatment (6 months), the DCS (a) will contact the patient's primary care provider in person, by phone, or through the electronic medical record to notify the provider of the patient's high depressive symptoms and to urge the provider to follow-up and (b) will provide a list of local mental health services, including referral to a psychiatrist outside of the study team. In addition, participants in both treatment groups who continue to exhibit

elevated depressive symptoms (PHQ-9 ≥ 10) at post-treatment will be urged to follow-up with their primary care providers regarding their depression. Their providers will also receive a letter from the study team indicating that their patient has completed participation in the treatment phase of the trial and continues to have elevated depressive symptoms. This letter will also urge physicians to follow-up with their patients and will provide a list of local mental health services. Finally, for participants in both treatment groups who score in the “severe depression” range (20-27) on the PHQ-9 during an annual follow-up call, the DCS (a) will contact the patient’s primary care provider in person, by phone, or through the electronic medical record to notify the provider of the patient’s high depressive symptoms and to urge the provider to follow-up and (b) will provide a list of local mental health services, including referral to a psychiatrist outside of the study team.

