At the first session, the depression clinical specialist (DCS), a Master's-level licensed mental health counselor (LMHC), will review depression materials and discuss treatment options. The DCS will then work with the patient's primary care provider to develop a plan that follows the IMPACT algorithm⁶⁵ with modifications noted above. Our modernized algorithm recommends a Step 1 treatment of 8-12 weeks of BtB or an antidepressant depending on the patient preference. Providers will manage prescriptions. In addition to delivering PST-PC, the DCS will help the patient adhere to antidepressant therapy and schedule pleasurable activities. If the patient is taking an antidepressant at baseline, the dose will be increased, BtB will be added, or the antidepressant will be discontinued and another one will be prescribed or BtB will be delivered. If the patient wants psychotherapy but has a strong preference for traditional treatment, PST-PC will be offered at Step 1. The DCS will have weekly team meetings with the supervising psychiatrist ([name]) and primary care expert ([name]), during which new cases and those requiring plan changes will be discussed. Fidelity to the eIMPACT algorithm will be continually assessed and recorded by the supervisors at these team meetings, and adjustments needed to ensure high fidelity will be made.

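### Section 7.0(c) makes psychosis or bipolar disorder, as judged by the eIMPACT psychiatrist, a reason for study withdrawal with no follow-up rule, so 12-month outcomes could be lost unequally by arm

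*Combined protocol and SAP*

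**What the plan says.** Section 7.0 (Study Withdrawal/Discontinuation) adds three situations to withdrawal at the participant's own request, introduced by "Other reasons for study withdrawal/discontinuation are".

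- **(a)** A treating provider "no longer believes that his/her patient is appropriate for this trial after a triggering of the Suicidal Ideation Protection Protocol or any other reason".
- **(b)** Acute or serious illness rules out the main visits. The consequence is spelled out: "In the case of situation (b), the patient will not complete any future study visits or calls". With the patient's permission, "electronic medical record data (e.g., incident CVD events) will still be obtained going forward".
- **(c)** During the 1-year treatment phase, "the participant, in the assessment of the eIMPACT psychiatrist, exhibits evidence of a psychotic disorder or bipolar disorder". The reasons given are that these are conditions "both of which are exclusionary conditions and could interfere with treatment delivery/effectiveness", and that such patients would probably benefit from "psychotropic medications, such as antipsychotic medications or mood stabilizer, that are beyond what are provided in this trial". No sentence says what happens to the 12-month visit, the calls or record follow-up.

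The eIMPACT part of section 5.0 describes the psychiatrist's role: "The DCS will have weekly team meetings with the supervising psychiatrist", where new cases and cases needing a change of plan are reviewed. The same section says usual-care patients receive no depression treatment from the study team. Section 7.0 directs severe usual-care cases at 6 months to their own provider and to a psychiatrist outside the team. Section 3.0 excludes a history of bipolar disorder or psychosis. Section 8.0 declares intent-to-treat and plans two-sample t-tests on 12-month values.

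**The concern.** The reasons given for (c) justify stopping study treatment and referring the patient. They give no reason to stop measuring the patient. Because (c) stands in a list of study-withdrawal reasons, staff could reasonably apply it as an end to participation.

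The trigger is a judgment by a clinician attached to one arm's treatment. In eIMPACT, the depression clinical specialist (DCS) attempts contact at least every two weeks at the start and meets the psychiatrist weekly. The study contact described for usual care between the baseline and 12-month visits is one call at about 6 months, made by research assistants. An emerging manic or psychotic picture is therefore more likely to reach the named assessor from eIMPACT. In effect, (c) can work as an eligibility check after randomization that is applied mainly to one arm.

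A patient withdrawn before the 12-month visit has no value for the planned t-tests, and section 8.0 names no method for missing data. SCL-20 (Hypothesis 2) is the outcome most plausibly affected; flow-mediated dilation (FMD) may not be affected at all. If withdrawn patients would have scored worse, the comparison moves in favour of eIMPACT. That direction is plausible, but the documents do not show it. Harms collected by questionnaire could also be missed.

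**Working it through.** **The plan's own figures (section 8.0).** A two-sided t-test at 0.05 with d = 0.61 and 80% power needs 43.2, so 44 per arm, as stated. With 86 per arm (172/2), power is 0.978 for d = 0.61 and 0.801 for d = 0.43, matching the stated 0.98 and 0.80. This point disputes none of these numbers. They set the scale. (220 x 0.80 is 176 rather than the stated 172, which makes no difference here.)

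**SCL-20: inputs.** From the plan: 110 per arm (220/2), 86 completers per arm, and depressive-symptom effects of d = 0.69 and 1.33. Assumed, because the documents give no figures:

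- f = 1/110, 2/110 or 4/110, the share of each arm with an emerging disorder, all withdrawn if in eIMPACT
- k = 0 to 1.0, how many SD worse they would have scored
- r = 0 or 0.5, the share of usual-care counterparts who also leave, under (a) or (b)

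**Formula.** With no true effect, eIMPACT completers include none of these patients. Usual-care completers include the share p = f(1 - r)/(1 - fr). The bias in SD units is p x k.

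Example with f = 4/110, k = 1.0:
- r = 0: p = 0.0364, bias 0.0364
- r = 0.5: p = 0.0182/(1 - 0.0182) = 0.0185, bias 0.0185

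The chance of a significant result favouring eIMPACT (nominal 0.025) comes from 200,000 simulated trials per scenario, with 86(1 - fr) usual-care and 86(1 - f) eIMPACT patients.

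| eIMPACT patients withdrawn | k | r | Bias (SD) | P(significant, favouring eIMPACT) |
|---|---|---|---|---|
| 1 | 0.5 | 0 | 0.0045 | 0.027 |
| 1 | 0.5 | 0.5 | 0.0023 | 0.026 |
| 1 | 1.0 | 0 | 0.0091 | 0.029 |
| 1 | 1.0 | 0.5 | 0.0046 | 0.027 |
| 2 | 0.5 | 0 | 0.0091 | 0.028 |
| 2 | 0.5 | 0.5 | 0.0046 | 0.027 |
| 2 | 1.0 | 0 | 0.0182 | 0.033 |
| 2 | 1.0 | 0.5 | 0.0092 | 0.029 |
| 4 | 0.5 | 0 | 0.0182 | 0.032 |
| 4 | 0.5 | 0.5 | 0.0093 | 0.029 |
| 4 | 1.0 | 0 | 0.0364 | 0.043 |
| 4 | 1.0 | 0.5 | 0.0185 | 0.033 |

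With k = 0 the bias is 0 and the probability is about 0.025.

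**Check of the largest entry.** SE = sqrt(2/86) = 0.1525 and 0.0364/0.1525 = 0.239. The normal probability below -1.960 + 0.239 = -1.721 is 0.043.

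**Relative size.** 0.0023/0.69 = 0.3%; 0.0364/0.69 = 5.3%; 0.0364/1.33 = 2.7%. With r = 0, a bias of 0.05 SD would need 0.05/1.0 x 110 = 5.5 (about 6) withdrawals at k = 1.0, or 0.05/0.5 x 110 = 11 at k = 0.5.

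**FMD, if it were affected.** Take 88 completers per arm (176/2) and remove m eIMPACT patients whose FMD averages g SD below the rest of their arm. The shift is g x m/88. For m = 1 to 5 and g = 0.25 to 1.0 this is 0.003 to 0.057 SD. The implied SD is 1.7/0.61 = 2.79 points, so the shift is 0.01 to 0.16 points against a target of 1.7. At m = 5, power for d = 0.43 falls from 0.810 to 0.798; for d = 0.61 it stays above 0.97.

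**Questionnaire-reported harms.** A patient withdrawn before month 6 would miss the 6-month call, the 12-month visit and 2 to 4 annual calls, so 4 to 6 adverse-event questionnaires.

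**The case against.** The strongest reply is that only (b) expressly ends visits and calls. The silence on (c), together with its treatment-based reasons and a section title that also covers discontinuation, allows (c) to be read as stopping treatment only. That reading is open, and the consent statement and authorization form that section 7.0 mentions were not available to this review. But (c) shares its lead-in with (a) and (b), so the opposite reading is just as natural.

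Second, (c) names no arm, and usual-care cases have other ways out: (a) lets any treating provider end participation, severe 6-month scores prompt provider contact and referral, and psychiatric updates are asked in both arms. This stands as a limit. The supportable claim is unequal detection, not removal from one arm only, and r = 0.5 in the working allows for it.

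Third, few cases are likely, because known history is excluded at entry. That also stands.

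Fourth, the analysis section does not exclude withdrawn patients, so the intent-to-treat problem is at bottom a missing-data gap affecting all of the planned 20% attrition, of which (c) would be a small part. This is fair. Still, losses under (c) would come from a protocol rule tied to arm, and they can be avoided.

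Finally, the searches of the Indiana Network for Patient Care (INPC) for emergency visits, hospitalizations and deaths need no patient participation and are not said to stop, and the data and safety monitoring board reviews retention every 6 months. Serious harms and most cardiovascular events may therefore still be captured.

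**Conclusion.** The concern holds. Section 7.0(c) is written as a reason for study withdrawal, has no follow-up rule, and depends on a clinician described as reviewing only eIMPACT cases. Unequal detection is an inference from those facts, but a well-supported one.

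The true size is unknown and probably small. Under the assumed 1 to 4 withdrawals and k = 0.5 to 1.0, the SCL-20 bias is 0.002 to 0.036 SD, or 0.3% to 5.3% of d = 0.69. The chance of a false positive favouring eIMPACT rises from 2.5% to between 2.6% and 4.3%. With k = 0 there is no bias. Nothing in the documents supports the 6 to 11 withdrawals that a 0.05 SD bias would need. The trial's conclusions are not threatened; the change is worth making because it is cheap and brings section 7.0 into line with intent-to-treat.

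**What to change.** Reword 7.0(c) along these lines: evidence of a psychotic or bipolar disorder stops study-delivered depression treatment and leads to referral, but does not end study follow-up. Unless consent is withdrawn, the patient stays in the assigned arm and completes the 6-month call, 12-month visit, annual calls and INPC searches. A patient too ill to attend is handled under (b), including its record follow-up with permission. Report by arm the number leaving under each of (a), (b) and (c).

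The cost is a sentence or so of protocol text plus follow-up of a few patients already counted in the 220. Using the plan's payments for a patient identified before month 6:

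- with 2 annual calls: $25 + $100 + $40 + $10 = $175
- with 4 annual calls: $25 + $100 + $80 + $10 = $215

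For 1 to 4 patients that is $175 to $860 (4 x $215). The downsides are some voluntary burden on unwell patients, and an estimate that includes patients whose study treatment was stopped, as intent-to-treat requires. Sample size, endpoints and tests do not change.
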